**Table 1: Time and Events Schedule Overview**

As of Amendment 5, refer to [Attachment 4](#) for a description of dose administration and study procedures for subjects who continue in the Treatment Extension Phase or who have discontinued treatment but remain in Follow-up.

|   |  | Screening Phase                     | Treatment Phase (including treatment extension/re-initiation phase)                      | EOT                            | Follow-up |
|---|--|-------------------------------------|--|--------------------------------|-----------|
|   | Notes  | within 28 days before randomization | 8-week cycles  | at 28 ± 7 days after last dose |           |
| Study treatment should be initiated within 5 days after randomization. The start of each cycle may occur ±5 days of the scheduled day in order to accommodate the schedule of the site or subject. After EOT, subjects in all treatment arms prior to PD will continue to return for disease evaluations. After PD is documented, subjects will be followed for survival; subsequent anticancer therapy, and occurrence of other malignancy. Follow-up visits, unless otherwise specified, are at Week 5, Week 9, and then q8wks during the first year after subject's first dose, then q16wks until PD and q6mos after PD. |  |                                     |  |                                |           |
| Procedures   |  |                                     |  |                                |           |
| Informed consent  | ICF must be signed before any study-related procedures are performed.  | X                                   |  |                                |           |
| Eligibility criteria  |  | X                                   |  |                                |           |
| Demography/
Medical History  |  | X                                   |  |                                |           |
| Chest X-ray   | Acceptable for screening if performed as part of SOC within 42 days before randomization   | X                                   |  |                                |           |
| FEV1 test   | Subjects with COPD   | X                                   |  |                                |           |

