|  | Notes  | within 28 days before randomization | 8-week cycles   | at 28 ± 7 days after last dose     |           |
| HBV DNA test   | For subjects with serologic evidence of resolved HBV infection (ie, positive Anti-HBs or positive Anti-HBc) at Screening, HBV DNA testing by PCR must be performed locally. Refer to Section 9.5.2.  |                                     | Prior to re-initiation, Q12W during treatment, at the End of Treatment Visit, and Q12W for up to 6 months after the last dose of study treatment  |                                    |           |
| Serum chemistry  |  | X                                   | Please see Table 3 for details.   |                                    |           |
| Whole blood  | Plasma and PBMC biomarker assessments  |                                     | C1D1, C4D1  | X                                  |           |
| Whole blood  | Immunophenotyping  |                                     | C1D1, C2D1, C4D1, C8D1  | X                                  |           |
| Daratumumab PK   | During treatment phase, 1 sample to be collected before start (window -2 hrs) and 1 sample immediately after end (window +2 hrs) of dara infusion. For subjects in QTc substudy, see Table 2 for collection on C1D1 and C1Wk8. Samples to be sent to central laboratory.       |                                     | Arm A: C1D1, C1Wk8 (day of Dose #8), C2D1, C3D1, C4D1, C6D1, C8D1
Arm B: C1D1, C1Wk8, C2D1, C3D1, C4D1, C6D1
Arm C: C1D1, C1Wk8   | 4wks and 8wks after last dara dose |           |
| Daratumumab immunogenicity   | No additional sample needed for planned timepoints; will be taken from PK sample. All planned treatment phase timepoints are pre-dose only.  |                                     | Arm A: C1D1, C2D1, C4D1, C6D1
Arm B: C1D1, C2D1, C4D1, C6D1
Arm C: C1D1, C1Wk8
If an infusion reaction occurs, obtain unscheduled blood sample as soon as possible.                                    | 4wks and 8wks after last dara dose |           |
| Disease Evaluations: Subjects in Arm C will continue disease assessments per schedule below after completion of treatment in Cycle 1. For all subjects, every effort should be made to conduct disease evaluations as per schedule (window ±7 days). Refer to Section 9.2 for details |  |                                     |   |                                    |           |

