| MRI of spine and pelvis              | Screening assessment may be performed within 56 days before randomization  | X  | q6 months for the first 3 years, then q12 months, and at biochemical progression (eg, increase in SPEP >25%) or at suspected PD; whole body MRI per local practice or when clinically indicated.  |                                |           |
| Second primary malignancy            |  |  |   |                                | X         |
| Subsequent Anti-myeloma Therapy      | Record both treatment and response.  |  |   |                                | X         |
| Survival                             |  |  |   |                                | X         |
| Ongoing Subject Review        |  |  |   |                                |           |
| Adverse Events                       | See Section 12 for detailed instructions.  | continuous from the time of signing of ICF until 30 days after last dose of last study treatment |   |                                |           |
| Concomitant Medications              | See Section 8 for detailed instructions.   | continuous from the time of signing of ICF until 30 days after last dose of last study treatment |   |                                |           |

Abbreviations: AE=adverse event; C=cycle; CMMCs: circulating multiple myeloma cells; COPD=chronic obstructive pulmonary disease; CR=complete response; ECOG=Eastern Cooperative Oncology Group; D=day; Dara=daratumumab; ECG=electrocardiogram; EOT= End-of-Treatment; FEV= Forced Expiratory Volume (in 1 second); FFPE=formalin-fixed paraffin embedded; FLC=free light chain; IAT= indirect antiglobulin test; ICF=informed consent form; IFE=immunofixation; MRD=minimal residual disease; MRI=magnetic resonance

imaging; PBMC= peripheral blood mononuclear cell ; PK=pharmacokinetics; PD= disease progression; SAE=serious adverse event; SOC=standard of care; SPEP=serum M-protein quantitation by electrophoresis; UPEP=urine M-protein quantitation by electrophoresis; Wk=week

- a Includes HBsAg, anti-HBs, and anti-HBc. For subjects who enter extension treatment period, HBV serology (HBsAg, anti-HBs, and anti-HBc) testing is to be performed locally prior to re-initiation. HBV serology is not required at re-initiation if this was performed as part of standard of care within 3 months prior to the re-initiation or the start of extension treatment is within 3 months of last daratumumab dose.

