### **Adverse Events**

Adverse events (with the exception of progression of MM) will be reported by the subject (or, when appropriate, by a caregiver, surrogate, or the subject's legally acceptable representative) for the duration of the study. Adverse events will be followed by the investigator as specified in [Section 12](#), Adverse Event Reporting.

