### HBV serology

For subjects who enter extension treatment period, HBV serology (HBsAg, anti-HBs, and anti-HBc) testing is to be performed locally prior to re-initiation. HBV serology is not required at re-initiation if this was performed as part of standard of care within 3 months prior to the re-initiation or the start of extension treatment is within 3 months of last daratumumab dose. For subjects with evidence of positive HBV serology, monitor for clinical and laboratory signs of HBV reactivation during treatment (Q12W), and for at least 6 months (Q12W) following the end of study treatment.

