### **12.3. Procedures**

#### **12.3.1. All Adverse Events**

All adverse events and special reporting situations, whether serious or non-serious, will be reported from the time a signed and dated ICF is obtained until 30 days after the last dose of study treatment, unless the subject withdraws consent for study participation, or starts subsequent anticancer therapy. For subjects who have received subsequent treatment with therapeutic intent for MM during the adverse event reporting period, only adverse events that are considered to be possibly, probably, or definitely related to daratumumab need to be reported. Serious adverse events, including those spontaneously reported to the investigator within 30 days after the last dose of study treatment, must be reported using the Adverse Event Form. The sponsor will evaluate any safety information that is spontaneously reported by an investigator beyond the time frame specified in the protocol.

Disease progression should not be recorded as an adverse event or serious adverse event term; instead, signs and symptoms of clinical sequelae resulting from disease progression/lack of efficacy will be reported if they fulfill the serious adverse event definition (refer to Section 12.1.1). Death should not be recorded as an adverse event or serious adverse event, but as the outcome of an adverse event. The adverse event that resulted in the death should be reported as a serious adverse event. All events that meet the definition of a serious adverse event will be reported as serious adverse events, regardless of whether they are protocol-specific assessments.

All adverse events, regardless of seriousness, severity, or presumed relationship to study treatment, must be recorded using medical terminology in the source document and the eCRF. Whenever possible, diagnoses should be given when signs and symptoms are due to a common etiology (eg, cough, runny nose, sneezing, sore throat, and head congestion should be reported as "upper respiratory infection"). Investigators must record in the eCRF their opinion concerning the relationship of the adverse event to study therapy. All measures required for adverse event management must be recorded in the source document and reported according to sponsor instructions.

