6.1. Adverse Events

AEs will be monitored throughout the study. All AEs will be recorded in standard medical terminology and graded according to the National Cancer Institute Common Terminology Criteria for Adverse Events (NCI-CTCAE), Version 4.03. Each occurrence of a given AE will be recorded with the NCI-CTCAE grade. Only the most severe grade over the course of a given episode will be reported. For AE reporting, adverse events will be coded using the latest version of Medical Dictionary for Regulatory Activities (MedDRA) coding dictionary.

All summaries of AEs will be based on treatment-emergent adverse events (TEAEs), defined as any AE that occurs after the first administration of study agent through 30 days after the last study agent administration; or any AE that is considered drug-related (very likely, probably, or possibly related) regardless of the start date of the event; or any AE that is present at baseline but worsens in toxicity grade or is subsequently considered drug-related by the investigator.

The incidence of TEAEs will be summarized overall, by MedDRA system organ class (SOC) and preferred term, by toxicity grade, and by relationship to study agent administration. Specifically, the following AE summaries will be presented:

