6.4. Clinical Laboratory Tests

The evaluation of clinical laboratory tests will focus on the following selected laboratory analytes:

- Hematology panel: hemoglobin, WBC count, neutrophils (ANC), absolute lymphocyte count (ALC) and platelet count
- Blood chemistry panel: uric acid, total bilirubin, creatinine, BUN, AST, ALT, and alkaline phosphatase, LDH, potassium, sodium, magnesium, calcium

Descriptive statistics (mean, standard deviation, median, minimum and maximum) will be used to summarize laboratory values and change from baseline at each scheduled visit up to Cycle 24 for each treatment group. Line plots of mean with standard deviation of laboratory values over time up to Cycle 20 will be displayed by treatment group for hemoglobin, neutrophils, platelets, AST, ALT, alkaline phosphatase.

The worst toxicity grade in hematology, chemistry, will be summarized by treatment group and toxicity grade. Shift tables from baseline to worst toxicity grade will be provided for laboratory parameters listed above. These tables will summarize the number of subjects with each baseline CTC grade and changes to the maximum CTC grade.

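### The sections disagree on when adverse-event recording ends (30 days after the last dose, or the whole study), so capture of a late, non-serious hepatitis B reactivation found by the scheduled tests is not assured

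*Protocol*

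**What the plan says.** **Reporting window, 30 days.** Protocol 12.3.1 covers all adverse events, serious and non-serious, "reported from the time a signed and dated ICF is obtained until 30 days after the last dose of study treatment". The adverse-event row of Table 1 reads "continuous from the time of signing of ICF until 30 days after last dose of last study treatment", and Attachment 4, the schedule in force since Amendment 5, repeats it. The note to the adverse-event definition in 12.1.1 sends the reader to 12.3.1 for the time of last recording.

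**Reporting window, whole study.** Section 9.5.2 (Adverse Events) has events reported by the subject or a "legally acceptable representative) for the duration of the study". The opening of 9.5.2 sends clinically relevant changes that occur during the study to the adverse-event section of the eCRF. Section 12.3.2 requires reporting of all serious adverse events that occur during the study and sets no 30-day limit.

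**HBV follow-up.** Table 1 and Attachment 4 require HBV DNA tests, in subjects with serologic evidence of resolved infection, during treatment, at the End-of-Treatment visit and then "Q12W for up to 6 months after the last dose of study treatment". Section 9.5.2 (HBV serology) asks for monitoring during treatment "and for at least 6 months (Q12W) following the end of study treatment".

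**Analysis.** SAP 6.1 counts as treatment-emergent any event up to 30 days after the last dose, "or any AE that is considered drug-related (very likely, probably, or possibly related) regardless of the start date of the event". The SAP 6.4 analytes are a haematology panel and "Blood chemistry panel: uric acid, total bilirubin, creatinine, BUN, AST, ALT, and alkaline phosphatase, LDH, potassium, sodium, magnesium, calcium". HBV DNA is not among them.

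**The concern.** The amendment log gives the identification of HBV reactivation as a new important risk among the reasons for Amendment 4, which added Section 8.3 and the HBV testing. The protocol therefore looks for this harm for about six months after treatment, while the section it names as governing adverse-event recording stops at Day 30.

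A positive result after Day 30 has no stated destination. HBV DNA is tested locally, so it does not arrive through the central-laboratory transfer described in 17.6. In Attachment 4 the haematology, bone marrow and imaging rows tell the site to enter results in the CRF; the HBV DNA row does not. Routine concomitant-medication collection (Section 8) also ends by Day 30. Section 8.3 deals with reactivation while on treatment.

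At stake is whether the final safety report describes post-treatment reactivation completely. Amendment 6 extended the study partly to collect long-term safety data.

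**Working it through.** The documents give no figure to reproduce. The check is day arithmetic and a comparison of passages.

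**Inputs**
- Adverse-event window: 30 days after the last dose (12.3.1, Table 1, Attachment 4).
- Test interval: 12 weeks = 12 × 7 = 84 days (Table 1, Attachment 4).
- End-of-Treatment visit: "at 28 ± 7 days after last dose" (Table 1).
- Six months = 180 to 184 days (assumption).

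**Post-treatment tests, counted from the last dose**
- First: Day 84, which is 84 − 30 = 54 days after the window closes.
- Second: Day 168, which is 168 − 30 = 138 days after it closes.

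If the 12-week rhythm is instead carried over from treatment, the first post-dose test could fall earlier, on some Day t between 1 and 84. The second is then on Day t + 84, between Days 85 and 168. At least one test still falls outside the window.

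**End-of-Treatment test**
- Permitted days: 28 − 7 = 21 to 28 + 7 = 35, or 15 days. Days 31 to 35 (5 of 15) are outside the window.
- This shows little, because a reactivation found on those days may have begun by Day 30.

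**Share of monitored days outside the 12.3.1 window**
- (180 − 30)/180 = 150/180 = 83.3%.
- (184 − 30)/184 = 154/184 = 83.7%.

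**What happens to a reactivation that begins after Day 30**

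| Event | 12.3.1, Table 1, Attachment 4 | 9.5.2 and 12.3.2 | SAP, if recorded |
|---|---|---|---|
| Serious | Outside the window | Reportable under 12.3.2 | Treatment-emergent if judged at least possibly related |
| Non-serious, clinically relevant | Outside the window | Eligible under 9.5.2 | As above |
| Non-serious, not judged clinically relevant | Outside the window | Only the general statement in 9.5.2 (Adverse Events), which refers to Section 12 for follow-up | As above |
| Any, judged doubtful or not related | Outside the window | As for its type above | Not treatment-emergent by date |

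The last two rows are the weakest. A site that follows the cross-reference in 12.1.1 stops at Day 30; a site that follows 9.5.2 does not.

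**SAP output.** The infection summary in SAP 6.3.2 covers Grade 3 or 4 treatment-emergent events only. The events of clinical interest in 6.3 are infusion-related reactions, infections and second primary malignancies. There is no HBV-specific table or listing.

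**The case against.** A reader might infer that reactivations found by the later tests are neither recorded as adverse events nor analysed. The documents do not support that.

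- **Recording.** Section 12.3.2 brings in serious events throughout the study. Section 9.5.2 sends clinically relevant changes to the adverse-event form. Section 11.8 does the same for laboratory changes that lead to a treatment intervention or concomitant therapy, and a reactivation that leads to antiviral treatment would fit. Section 12.3.1 itself has the sponsor evaluate late spontaneous reports.
- **Analysis.** The drug-related part of the SAP 6.1 definition has no time limit, so a recorded event judged at least possibly related enters the treatment-emergent tables.

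These points stand, and they rule out the absolute reading. They do not remove the gap. The study-long passages conflict with 12.3.1 instead of overriding it, 12.1.1 points to 12.3.1, and no rule obliges a site to send a late spontaneous report.

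It is also fair to say that the SAP could hardly list HBV DNA. Its text appears to predate Amendment 4 (January 2019): SAP 1.2 still has whole-blood MRD, which Amendment 3 removed in June 2017, and an end of study at about 4 years. The missing HBV output is therefore a reason to update the plan for the final analysis, not an oversight when it was written.

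Finally, the affected group may be small. Subjects positive for HBV DNA are excluded under criterion 6.1, Table 1 schedules serology only at re-initiation, and treatment extension is limited to Arms A and B. A 30-day window for general adverse events is a legitimate design choice and is not criticised here.

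**Conclusion.** The point holds in a limited form. The protocol states the reporting period in two ways, and under the section it names as governing, a non-serious HBV reactivation that begins after Day 30 need not be recorded, although the scheduled tests may find it. Capture is not assured; it is not ruled out either.

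The gap is 150 to 154 of 180 to 184 post-dose days (83% to 84%). It would be tempting to read this as the share of reactivations missed. That would require onsets spread evenly over the six months and none of the other recording routes to operate, and the documents establish neither. The number of subjects affected cannot be computed, because no HBV seroprevalence or count of tested subjects is given. The test days assume counting from the last dose; the conclusion does not depend on this, since at least one test falls after Day 30 on either counting.

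The change is worth making because it costs little and concerns a risk the sponsor calls important.

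**What to change.** 1. Reconcile 12.3.1, Table 1 and Attachment 4 with 9.5.2 and 12.3.2. Keep the 30-day window for other adverse events, and say explicitly which period applies to serious events and to clinically relevant changes, so that the alignment does not close the 12.3.2 route by accident.
2. State that HBV reactivation, serious or not, found by the tests already scheduled is recorded on the adverse-event eCRF to the end of the protocol's HBV monitoring period. Add a matching CRF instruction to the HBV DNA row of Attachment 4. Second primary malignancy, already collected during Follow-up, is a model. There is no need to extend collection to every drug-related event.
3. Reconcile the minimum of six months in 9.5.2 (HBV serology) with the maximum of six months in Table 1 and Attachment 4. This review does not choose between them.
4. For the final analysis, add a listing of HBV reactivation among subjects tested, with time since last dose.

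The cost is protocol wording, one event type kept open on an existing form, a few late events to enter and one listing. No test or visit is added.

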### **12.3.2. Serious Adverse Events**

All serious adverse events occurring during the study must be reported to the appropriate sponsor contact person by study-site personnel within 24 hours of their knowledge of the event.

Information regarding serious adverse events will be transmitted to the sponsor using the Serious Adverse Event Form, which must be completed and signed by a physician from the study site, and transmitted to the sponsor within 24 hours. The initial and follow-up reports of a serious adverse event should be made by facsimile (fax).

All serious adverse events that have not resolved by the end of the study, or that have not resolved upon discontinuation of the subject's participation in the study, must be followed until any of the following occurs:

- The event resolves
- The event stabilizes
- The event returns to baseline, if a baseline value/status is available
- The event can be attributed to agents other than the study drug or to factors unrelated to study conduct
- It becomes unlikely that any additional information can be obtained (subject or health care practitioner refusal to provide additional information, lost to follow-up after demonstration of due diligence with follow-up efforts)

Suspected transmission of an infectious agent by a medicinal product will be reported as a serious adverse event. Any event requiring hospitalization (or prolongation of hospitalization) that occurs during the course of a subject's participation in a study must be reported as a serious adverse event, except hospitalizations for the following:

- If the subject has not experienced a significant medical event but is hospitalized overnight only for observation following administration of daratumumab, then the hospitalization should not be reported as a serious adverse event.

- Hospitalizations not intended to treat an acute illness or adverse event (eg, social reasons such as pending placement in long-term care facility)
- Surgery or procedure planned before entry into the study (must be documented in the eCRF). Note: Hospitalizations that were planned before the signing of the ICF, and where the underlying condition for which the hospitalization was planned has not worsened, will not be considered serious adverse events. Any adverse event that results in a prolongation of the originally planned hospitalization is to be reported as a new serious adverse event.

